Protocol Title: Singlet oxygen quantification after skin exposure to ultraviolet A (UVA) light

1) Protocol title: Singlet oxygen quantification after skin exposure to ultraviolet A (UVA) light

Protocol version date: May 11, 2017

2) Objectives

The objective of this study is quantification of singlet oxygen species in the skin after exposure to UVA light

3) Background

Ultraviolet (UV) radiation can lead to skin damage and cancer. UVA irradiation is 10 to 100 times more abundant in natural sunlight than UVB, thus human skin is exposed to more UVA irradiation daily.(1-4) UVA irradiation is not completely filtered by clothing and it penetrates deeper into the dermis than UVB, potentially causing more damage.(3-5)

It is believed that skin cancer, photo aging, and skin immunomodulation are mediated by the reactive oxygen species (ROS) that are generated in response to UV radiation.(6) Singlet oxygen (${}^1\text{O}_2$) is one type of ROS.(6)

The aim of this study is to quantify the level of singlet oxygen generated in the skin after exposure to UVA radiation. Previous studies have used low dose UVA1 irradiation of 20 J/cm^2 , which mimics exposure to strong sunlight of approximately two hours.(4) This study will use UVA doses equivalent to or less than what humans are exposed to in daily life. Additionally, the aim is to quantify singlet oxygen produced in individuals of various skin types before and after application of sunscreens containing zinc oxide and avobenzone (SPF 30). To our knowledge, there is no method for quantifying singlet oxygen in human skin after exposure to UVA light. This is a novel method that may help us understand further the protective effects of various skin types, as well as sunscreens.

4) Inclusion and Exclusion Criteria

Inclusion criteria:

- Subjects aged 18 years and older

Exclusion criteria:

- Those who are currently smoking or have smoked within the past 3 years.
- Aspirin use
- Multivitamins and supplements that contain vitamin E
- Adults unable to consent

Protocol Title: Singlet oxygen quantification after skin exposure to ultraviolet A (UVA) light

- Individuals who are not yet adults (infants, children, teenagers)
- Pregnant women
- Prisoners

5) Study Timelines

The study will be conducted over the course of one year.

The duration of each subject's participation is approximately one week.

6) Study Endpoints

Primary study endpoints include:

- To quantify singlet oxygen generated by the skin after exposure to three different UVA radiation doses (each equivalent to or less than UVA dose encountered in daily life)

Secondary study endpoints:

- Difference in singlet oxygen generate between individuals of different skin types
- Difference in singlet oxygen generation with two different sunscreens (zinc oxide and avobenzone, each SPF 30) vs control
- Change in appearance of skin pigmentation

Protocol Title: Singlet oxygen quantification after skin exposure to ultraviolet A (UVA) light

7) Procedures Involved

Subjects meeting the inclusion criteria without any of the exclusion criteria will be enrolled into this study. Up to 17 subjects will be recruited into this study.

Group A: N=7 Fitzpatrick skin type I-II

Group B: N=5 Fitzpatrick skin type III-IV

Group C: N=5 Fitzpatrick skin type V-VI

All subjects will undergo the same procedures, as follows:

Visit 1:

- Informed consent
- Review medical history and concomitant medications
- Fitzpatrick skin type classification
- Three spots measuring 2cm² each will be marked on subject's left dorsal forearm and right dorsal forearm
- Each spot will be assigned numbers 1, 2, or 3.
- Each spot will be exposed to corresponding UVA dose.
- UVA exposure at each site and singlet oxygen measurements will be recorded
- Any one spot will be exposed to UVA for up to 5 minutes. The exposure at any one skin site will range from 0.33 J/cm², 8.25 J/cm², and 16.5 J/cm². The exposures used in this study are below those normally used in the literature.(4)
- Subject will be compensated \$10 (gift card) at completion of the visit

Visit 2: May occur on the same day as Visit 1 up to 1 month after visit 1

- Three spots measuring 2cm² each will be marked on subject's left dorsal forearm and right dorsal forearm
- Each spot will be assigned numbers 1, 2, or 3.
 - First spot: control (no sunscreen)
 - Second spot: 2mg/cm² sunscreen with zinc oxide (SPF 30) will be applied
 - Third spot: 2mg/cm² sunscreen with avobenzone (SPF 30) will be applied
- Only one UVA dose will be used for all exposures. The dose will be chosen based on dose response during Visit 1 (either 8.25 J/cm² or 16.5 J/cm²)
- Any one spot will be exposed for up to 5 minutes

Protocol Title: Singlet oxygen quantification after skin exposure to ultraviolet A (UVA) light

- Subject will be compensated \$15 (gift card) at completion of the visit
- This completes subject's involvement in the study

Subject compensation is outlined as follows:

Visit 1: \$10

Visit 2: \$15

Protocol activity	VISIT 1	VISIT 2
Informed Consent	X	
Medical History	X	
Review concomitant Medication	X	
Mark 3 areas measuring 2cm ² each on right and left dorsal forearm	X	X
Expose each of the 3 marked skin areas to one UVA dose (0.33 J/cm ² , 8.25 J/cm ² , and 16.5 J/cm ²)	X	
Determine best UVA dose for subject based on dose response data	X	
Weigh sunscreen 2mg/cm ²		X
Apply zinc oxide containing sunscreen to one marked spot on each arm		X
Apply avobenzone containing sunscreen to one marked spot on each arm		X
Mark one spot as "control" (no sunscreen)		X
Expose each of the 3 marked skin areas to one UVA dose (as determined during visit 1)		X

8) Data and/or Specimen Management and Confidentiality

All data will be coded for the safety of the study subjects. Research data will only be available to the listed research personnel. The research site will maintain appropriate medical and research records for this study in compliance with ICH E6,

Protocol Title: Singlet oxygen quantification after skin exposure to ultraviolet A (UVA) light

Section 4.9 and regulatory and institutional requirements for the protection of confidentiality of subjects.

All of the study data will be coded and stored within a locked cabinet within a locked room with two levels of keyed entry required to gain access. Furthermore, data files will either be stored in password-protected files within a locked room that will require two levels of keyed entry for access.

Precaution will be taken to maintain the privacy of the participants. These include the following: All subjects will be assigned a subject ID number after signing the consent form. This will be their only form of identification throughout the remaining of the study period. Each subject's name, age, and medical record number will be recorded. The consent forms will be kept in a binder. The subjects will be entered into the data analysis sheets as subject ID numbers and a separate password-protected file will contain the key for these codes. All of the files will be saved on password-protected computers within locked rooms. All study related material will be kept in a locked cabinet within a locked room at UC Davis Department of Dermatology. Only the research team personnel will have access to study-related materials. Participant information will not be disclosed to third party individuals except for those authorized to oversee the research project.

Data that are already collected will not be destroyed but will be stored in a codified format that will not allow linkage to identifying information.

The singlet oxygen data are immediately stored after capture into a password-protected computer that will be stored in a locked room within the Institute for Regenerative Cures (IRC) at UC Davis. All data stored in binders will be transported to the UC Davis Clinical Trials unit (CTU).

Each of the subjects' signed consents will be filed in a locked cabinet within a locked room. All of the subjects' data will be entered into the data analysis sheets as codes and a separate password protected file will contain the key for these codes. All of the files will be saved on computers that will be within locked rooms. The research team will follow the UC Davis Institutional Policy for data security to ensure that all subjects and collected data are protected.

Protocol Title: Singlet oxygen quantification after skin exposure to ultraviolet A (UVA) light

9) Data and/or Specimen Banking

All patient information will be only accessible to authorized research personnel, and otherwise personalized information will be locked in a cabinet and password protected electronic drive at the UC Davis Department of Dermatology (IRC and CTU). After the study has been completed and analyzed, all patient information will be discarded. The code keys will be stored in a secure file in a password-protected computer in a locked room and this code key will be deleted upon completion of the analysis.

10) Provisions to Monitor the Data to Ensure the Safety of Subjects

The records and study materials will be maintained in a locked cabinet. Subjects will be asked about their health and any adverse events that may have occurred. Adverse effects will be related to the treating physician. Noted and serious adverse effects will be relayed to the IRB within 24 hours of the occurrence.

11) Withdrawal of Subjects

The subjects may withdraw consent at any time and they will be reassured that their clinical care will not be compromised if a subject were to withdraw. Subjects will be withdrawn from the study if they develop adverse side effects. The investigator can remove the subject from the study. Possible reasons for removal include:

- Failure to follow protocol
- Hypersensitivity to sunscreen

12) Risks to subjects

Subjects will be counseled that the physical risks from sunscreen application may include skin redness or irritation. The physical risks from UVA light may include mild redness or tanning of the spot exposed to UVA light. Subjects will be advised to inform the research team if they experience any side effects.

Although provisions are put in place to protect identifiable data, we cannot guarantee absolute protection of the data collected from each subject. Accordingly, the subjects will be informed of this risk.

13) Potential Benefits to Subjects

There are no direct benefits to the subjects.

Protocol Title: Singlet oxygen quantification after skin exposure to ultraviolet A (UVA) light

This study will help us add to the general scientific knowledge that may benefit individuals in the future.

14) Sharing of Results with Subjects

Any peer reviewed manuscripts that result from the study will be made available to the subjects on request.

15) Provisions to Protect the Privacy Interests of Subjects

Steps will be taken to protect subjects' privacy interests. Subjects will only interact with approved study personnel who have successfully completed human subjects training. This includes those involved in the study visits, consent, and in any study related procedures. We will do our best to make sure that the personal information in the subject's record is kept private. However, no study can guarantee 100% protection of private information despite all of our measures to protect each subject's privacy. Subjects will be made aware of this during the consent process.

16) Compensation for Research-Related Injury

If a subject is injured as a result of being in this study, the University of California will provide necessary medical treatment. Depending on the circumstances, the costs of the treatment may be covered by University or the study sponsor or may be billed to the subjects' insurance company just like any other medical costs. The University and the study sponsor do not normally provide any other form of compensation for injury. For more information about compensation, call the IRB administration at [contact] or email at [contact].

17) Economic Burden to Subjects

Standard of care and other routine costs will be billed to the patient or the patient's insurance carrier, Medicare, or Medi-Cal where appropriate. Only the costs of research and experimental procedures will be paid by the sponsor/department. Subjects may incur a cost in relation to travel needed to get to the UC Davis Dermatology Department for each visit.

18) Drugs or Devices

- I confirm that all investigational drugs will be received by the IDS pharmacy, which will store, handle, and administer those drugs so that they will be used only on subjects and be used only by authorized investigators.

Protocol Title: Singlet oxygen quantification after skin exposure to ultraviolet A (UVA) light

- ☒ I confirm that all investigational devices will be labeled in accordance with FDA regulations and stored and dispensed in such a manner that they will be used only on subjects and be used only by authorized investigators.

Device used in the study:

SINGLET OXYGEN MONITOR FOR UVA-SKIN STUDIES

The UVA-produced Singlet Oxygen monitor detects the weak, near infrared luminescence from the $a\rightarrow X$ system in molecular oxygen. It uses an ultra-sensitive photomultiplier tube (PMT) coupled to a photon counting system to monitor this weak emission produced by the UVA source that is also part of the system. This non-imaging, point sensor is an ultra-sensitive portable and automated real-time detection system for singlet O_2 . The current system includes (1) a fiber –coupled CW UVA source module, (2) PMT detector module, and (3) data acquisition with photon counter board.

A block diagram of the major components of the singlet oxygen sensor is shown in Figure 5.

[figure not shown]

Figure 1. Block diagram of the singlet oxygen monitor.

Protocol Title: Singlet oxygen quantification after skin exposure to ultraviolet A (UVA) light

[figure not shown]

Figure 2. Fiber coupled UVA light source and light box. Subjects insert their arms through the right side of the light box. The equipment rack including the PC screen is shown in the background.

References:

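### Section 4 does not exclude photosensitive disorders or photosensitising drugs, and known sunscreen hypersensitivity is only a discretionary ground for removal in section 11

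*Protocol*

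**What the plan says.** Section 4 has one inclusion criterion, adult age, and seven exclusions: smoking now or within three years, aspirin, "Multivitamins and supplements that contain vitamin E", inability to consent, minority, pregnancy and imprisonment. The only drugs or supplements named are aspirin and vitamin E products.

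Section 7 turns the lists into an enrolment rule: "Subjects meeting the inclusion criteria without any of the exclusion criteria will be enrolled into this study". It continues: "All subjects will undergo the same procedures, as follows". Visit 1 begins with consent and an instruction to "Review medical history and concomitant medications", followed by UVA at 0.33, 8.25 and 16.5 J/cm². Visit 2 uses one dose, 8.25 or 16.5 J/cm², on a bare control spot, a zinc oxide spot and an avobenzone spot. On timing, Visit 2 "May occur on the same day as Visit 1 up to 1 month after visit 1". At its end, "This completes subject's involvement in the study".

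Section 11 has two routes out of the study. One is mandatory: "Subjects will be withdrawn from the study if they develop adverse side effects". The other is permissive: "The investigator can remove the subject from the study". Sunscreen hypersensitivity is one of the examples listed under the permissive route. Photosensitivity is not listed.

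**The concern.** The study irradiates skin and applies two sunscreens. The volunteers most foreseeably at risk are those who already react abnormally to light, those taking a drug that makes them do so, and those already known to react to a sunscreen. The eligibility lists contain none of the three. Because section 7 enrols whoever passes the lists and treats all alike, following the protocol as written admits these volunteers and exposes them.

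What is at stake is subject safety. Section 13 offers subjects no direct benefit, so nothing offsets a risk that could be screened out beforehand. Sections 3 and 6 describe the doses as no higher than everyday exposure. That reassures for ordinary skin, but does not address people who react to ordinary sunlight or to sunscreen.

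Eligibility belongs in the protocol, so a statistical analysis plan would not be expected to supply these exclusions.

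**Working it through.** No sample-size or error-rate formula applies. The check sets the safeguards side by side and then describes the exposure.

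**1. Does any rule stop such a volunteer before exposure?**

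| Safeguard | Timing | Photosensitive disorder or drug | Known sunscreen hypersensitivity |
|---|---|---|---|
| Section 4 exclusions | Before enrolment | Not listed | Not listed |
| Section 7 history and medication review | Visit 1, before UVA | Would reveal it; no rule to act on | Would reveal it; no rule to act on |
| Section 11, permissive removal | Any time | Possible, since the list of reasons is open; not named | Named, but discretionary |
| Section 11, mandatory withdrawal | After an adverse effect | Only after a reaction | Only after a reaction |
| Section 10 health enquiry; section 12 counselling | Not tied to eligibility | No screening rule | No screening rule |

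No row requires that the volunteer be stopped before exposure. The review that would find the problem does have criteria to apply, but only for aspirin and vitamin E.

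**2. What does mandatory withdrawal still prevent?**

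- Visits on separate days: a reaction to Visit 1 UVA forces withdrawal before Visit 2, so the second round of UVA and all sunscreen are avoided. The Visit 1 doses have already been given.
- Visits on the same day: the rule can act only on a reaction that shows before Visit 2 starts.
- Sunscreen: it is first applied at Visit 2, which is the last visit. A reaction to it leaves little or nothing from which to withdraw.

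**3. What exposure does each subject receive?** This reads the procedures as three spots per arm, as the section 7 schedule implies by placing each sunscreen on one spot of each arm.

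- UVA exposures: 3 spots × 2 arms × 2 visits = 12.
- Visit 1 (6 exposures): 2 each at 0.33, 8.25 and 16.5 J/cm².
- Visit 2 (6 exposures at a single dose): 2 bare and 4 through SPF 30 sunscreen.
- Bare exposures at 16.5 J/cm²: 2 at Visit 1, plus 0 or 2 at Visit 2 depending on the dose chosen, so 2 to 4 in all.
- Sunscreen applications: 2 products × 2 arms = 4.
- Irradiated area: 6 spots × 2 cm² = 12 cm² per visit.

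**4. How large is the dose on the protocol's own scale?** Section 3 equates 20 J/cm² of UVA1 with about two hours of strong sun. Assuming proportionality and treating UVA1 as UVA, minutes = dose / 20 × 120:

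- 0.33 J/cm²: 0.33/20 × 120 ≈ 2 minutes
- 8.25 J/cm²: 8.25/20 × 120 = 49.5 minutes
- 16.5 J/cm²: 16.5/20 × 120 = 99 minutes

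Section 7 allows at most 5 minutes of exposure per spot. These figures describe dose on a small spot, not harm.

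**The case against.** The strongest reply is that much of the gap is already covered.

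- **Sunscreen hypersensitivity is named in section 11**, apart from the sentence on adverse effects, and nothing limits it to reactions arising on study. A known case found at Visit 1 could be removed before any sunscreen is applied. This stands: a reader might infer that the protocol ignores known sunscreen hypersensitivity, and that would be wrong. What remains is that removal is left to discretion.
- **The investigator may also act on photosensitivity**, because the section 11 reasons are only examples. This stands too. The documents do not support the inference that such a volunteer must be treated whatever the investigator thinks. They show only that no criterion requires that the volunteer be stopped.
- **Same-day visits are the worst case.** Visit 2 may follow up to a month later, and section 5 puts participation at about a week. With separated visits mandatory withdrawal does limit further UVA. It does not undo the Visit 1 doses and does not help with sunscreen.
- **The exposure is modest.** Quoting 12 exposures alone would mislead, since two are at 0.33 J/cm² and four are through sunscreen, all on 2 cm² spots. Section 12 expects only irritation and slight reddening or tanning. This limits the weight of the point, but section 12 says nothing specific about photosensitive people.
- **No estimate is affected.** Correct. A reader might infer that admitting such volunteers would bias the singlet oxygen measurements. The documents give no basis for a direction or size of such an effect, and none is claimed here.

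**Conclusion.** The point holds as a subject-safety gap. Photosensitive disorders and photosensitising drugs are not exclusions anywhere in the protocol. Known sunscreen hypersensitivity is a discretionary ground for removal and not an eligibility criterion. The section 7 enrolment rule, followed literally, admits all three kinds of volunteer to UVA up to 16.5 J/cm² and to both sunscreens.

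The size is modest: 2 to 4 bare spots of 2 cm² per subject at the top dose, and 4 sunscreen applications, if there are three spots per arm. A reader might want the number of the 17 subjects likely to be affected, or the chance of a reaction. The documents give no frequency for these conditions and no reaction rate, so neither can be derived. How serious a reaction would be is a clinical judgement that the documents do not inform.

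The change should still be made, because the risk is foreseeable, subjects have no direct benefit to set against it, and the step that would detect it is already scheduled.

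**What to change.** Add three exclusions to section 4: known hypersensitivity to any ingredient of the study sunscreens, photosensitive disorders, and current use of photosensitising drugs. The clinical investigators should set the exact list of disorders and drugs. State that the criteria are applied at the Visit 1 history and medication review, before any UVA is given. Keep the section 11 item for hypersensitivity that first appears on study.

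The cost is a few lines of text and no new procedure. The downside is that a few volunteers may be screened out and need replacing.

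### Visit 2 ties control, zinc oxide and avobenzone to spots 1, 2 and 3 in every subject, with no rotation of forearm position or reading order

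*Protocol*

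**What the plan says.** Section 7, Procedures Involved, opens the visit descriptions with "All subjects will undergo the same procedures, as follows". For Visit 2, three numbered spots are marked on each dorsal forearm and the conditions are listed against them: "First spot: control (no sunscreen"), "Second spot: 2mg/cm² sunscreen with zinc oxide (SPF 30) will be applied" and "Third spot: 2mg/cm² sunscreen with avobenzone (SPF 30) will be applied".

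The activity table in the same section is looser. It has entries such as "Apply zinc oxide containing sunscreen to one marked spot on each arm" and names no spot number. It therefore neither rotates the conditions nor overrides the list.

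Section 6 makes the comparison a secondary endpoint: "Difference in singlet oxygen generation with two different sunscreens (zinc oxide and avobenzone, each SPF 30) vs control".

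Section 18 describes the instrument: "This non-imaging, point sensor is an ultra-sensitive portable and automated real-time detection system".

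For Visit 1, Section 7 says "Each spot will be exposed to corresponding UVA dose" without listing which dose goes with which number.

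The protocol does not say how numbers map to places on the forearm, whether the second arm repeats or mirrors the first, or in what order the spots are exposed and read.

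**The concern.** The three spots on a forearm lie at different places, and a point sensor implies that they are read one after another. At up to 5 minutes per spot, six spots take up to 6 × 5 = 30 minutes of exposure in a visit. Signal could therefore differ between spots because of where they lie or when they are read, as well as because of sunscreen.

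If spot 1 is always in the same place and read first, and so on, any such difference has the same sign in every subject and goes straight into the sunscreen contrasts. Recruiting more subjects does not average it out. The analysis cannot separate it either, because data from this layout contain no forearm on which condition and position come apart. Allocation is settled when the spots are treated, so this cannot be left to a later analysis plan.

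**Working it through.** There is no figure in the protocol to reproduce on this point: it states no SD, drift, site gradient, test, significance level or power. The inputs taken from it are 7 + 5 + 5 = 17 subjects, two forearms each (34 forearms), three spots per forearm, and the fixed list above. Everything else below is assumed.

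**1. Can condition be separated from position?** Take a model with 34 forearm effects, 2 condition contrasts and 2 position contrasts, which makes 38 columns.
- Fixed list, same number-to-position link on every forearm: rank 36. The two position columns duplicate the two condition columns.
- Six possible orders rotated over the 34 forearms: rank 38. Both sets of effects can be estimated.

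**2. Size of the bias.** Let the signal shift by d per spot, linearly.
- Each arm read in the order 1, 2, 3: zinc oxide minus control is biased by 1d and avobenzone minus control by 2d.
- Arms alternated (left 1, right 1, left 2, and so on), with d the drift per reading: 2d and 4d.
- Second arm run in reverse: 0 and 0 for a linear shift.

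**3. What that could do to a test.** Assume no true sunscreen effect, a per-spot SD of s, two arms averaged, and a two-sided 5% paired t-test. The difference averaged over two arms has SD s × √(2/2) = s, so SE = s/√17. The rejection probability comes from the noncentral t distribution with 16 degrees of freedom and noncentrality bias/SE.

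| d per spot | Bias, zinc oxide / avobenzone | Rejection, s = 15% | Rejection, s = 25% |
|---|---|---|---|
| 1% | 1% / 2% | 5.8% / 8.1% | 5.3% / 6.1% |
| 3% | 3% / 6% | 12.1% / 34.1% | 7.5% / 15.4% |
| 5% | 5% / 10% | 25.3% / 73.3% | 12.1% / 34.1% |

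With 34 subjects instead of 17, at d = 3% and s = 15%, the rates rise from 12.1% to 20.5% and from 34.1% to 62.0%. The bias itself is unchanged; the test simply becomes surer of it.

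**4. Effect of rotating.** With the six orders spread as evenly as possible over 34 forearms, the bias in the allocation examined falls to 0 and 0.09d before any adjustment, and to 0 once position is in the model. Adjusting for position multiplies the variance of the contrasts by 1.000 (zinc oxide) and 1.0026 (avobenzone).

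**The case against.** The best counter-argument is that the protocol fixes labels, not locations. It never says that spot 1 is nearest the wrist, is read first, or sits in the same place on every arm, so the numbers may be no more than treatment codes. The activity table fits that looser reading. This stands as a limit: the confounding is left open, not proven, and the rank result depends on number following position or order. It does not remove the point, because the protocol then leaves protection to whatever staff happen to do.

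Second, no site or drift effect is documented, and a point sensor is not evidence of drift. That is correct. The rates above show what assumed values would do and no more; at d = 1% the harm is small. Reference readings, if taken, could correct instrument drift, but the protocol does not mention any, and they would not deal with differences between forearm sites.

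Third, the design has some protection: each subject is their own control, both arms are used, and all Visit 2 exposures use one dose. Using both arms balances left against right, but it does not separate condition from spot number when both arms carry the same numbering.

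Fourth, a large sunscreen effect could swamp the bias. That may hold for detecting any effect at all. The estimated protection would still be shifted, and unequally (1d against 2d), which would also distort any comparison of the two products.

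Finally, the case for Visit 1 is weaker. No dose-to-number pairing is listed, and the doses span 16.5/0.33 = 50-fold, so a drift of a few percent matters less there.

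**Conclusion.** The concern holds and should be fixed. As written, the plan gives every subject the same condition-to-spot list and has no safeguard against site or order effects in a named secondary endpoint. On the reading that number follows position or reading order, with each arm read 1, 2, 3, the bias is 1d for zinc oxide and 2d for avobenzone. Over the assumed range of d from 1% to 5% and SD from 15% to 25%, the false-positive rate runs from about 5% to 25% for zinc oxide and from about 6% to 73% for avobenzone, against a nominal 5%.

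The true size is unknown because the protocol gives neither d nor the SD. Confidence is moderate: the link from number to position or order is inferred, and the Visit 2 text bears on one secondary endpoint, not on the primary one. If the fixed list is followed, the fault could not be undone from the data once they are collected.

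**What to change.** Replace the fixed Visit 2 list in Section 7 with a pre-generated allocation:

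- Define positions 1 to 3 on the forearm and read the spots in position order, so that one list rotates both position and reading order.
- On each forearm, assign control, zinc oxide and avobenzone to the positions using the six possible orders, spread evenly over up to 34 forearms (34/6, so 5 or 6 per order).
- Balance approximately within skin-type group: 14 forearms in Group A give 2 or 3 per order, and 10 each in Groups B and C give 1 or 2. Use different orders on a subject's two arms.
- Assign the existing Visit 1 doses to spots in the same way, leaving the doses themselves unchanged.
- Record position and reading order, and include position in the model.
- Make the activity table refer to the allocation list.

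The cost is one list and one or two sentences in Section 7. No extra subjects, spots, exposure or visits are needed, and adjusting for position raises the variance of a sunscreen contrast by at most about 0.3%.

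### Does the withdrawal rule in Section 11 let the skin's reaction to UVA decide who reaches the Visit 2 sunscreen comparison?

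*Protocol*

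**What the plan says.** Section 11 (Withdrawal of Subjects) has two rules. The first is mandatory: "Subjects will be withdrawn from the study if they develop adverse side effects". The second is discretionary: "The investigator can remove the subject from the study", with failure to follow the protocol and sunscreen hypersensitivity as example reasons. Neither defines an adverse side effect.

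Section 12 (Risks to subjects) says: "The physical risks from UVA light may include mild redness or tanning of the spot exposed to UVA light". It then adds: "Subjects will be advised to inform the research team if they experience any side effects".

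Section 6 (Study Endpoints) lists among the secondary endpoints: "Change in appearance of skin pigmentation". The comparison of the two sunscreens with control is another secondary endpoint.

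Section 7 (Procedures Involved) gives all three UVA doses at Visit 1 and applies sunscreen only at Visit 2. Of Visit 2 it says: "May occur on the same day as Visit 1 up to 1 month after visit 1". On numbers: "Up to 17 subjects will be recruited into this study", split 7, 5 and 5 across Groups A, B and C. Section 5 expects each subject to take part for about one week.

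Section 8 (Data and/or Specimen Management and Confidentiality) says of the readings: "The singlet oxygen data are immediately stored after capture". It also says that data already collected are kept in coded form and not destroyed.

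**The concern.** The withdrawal sentence is mandatory and has no threshold. Section 12 names redness and tanning and then asks subjects to report side effects of any kind, so a reader may take those reactions to be side effects in the sense of Section 11. Tanning would then be both an outcome to observe and a reason for removal.

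Because UVA exposure at Visit 1 precedes sunscreen testing at Visit 2, the skin's response could decide who contributes to the sunscreen comparison. If reactions differ by Fitzpatrick type, the subjects at Visit 2 could differ in composition from those enrolled. With groups of 7, 5 and 5 and no stated replacement, a few losses would be noticeable. An analysis plan could not recover Visit 2 measurements that were never taken.

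**Working it through.** **The protocol's own figure.** Group sizes in Section 7: 7 + 5 + 5 = 17, which agrees with the stated maximum. The protocol gives no power, standard deviation, dropout or reaction rate, so there is nothing further to reproduce.

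**The passages side by side.**

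| Section | Term used | What it governs |
|---|---|---|
| 11, first rule | adverse side effects | mandatory withdrawal |
| 11, second rule | investigator may remove | discretionary withdrawal |
| 12, risk list | physical risks (mild redness, tanning) | counselling |
| 12, next sentence | any side effects | what subjects report |
| 6 | pigmentation change | secondary endpoint |

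No sentence says that the reactions listed in Section 12 are adverse side effects under Section 11, and none says that they are not. The reporting sentence omits the word adverse, which fits reporting being wider than withdrawal. The result is an undefined term, not two statements that cannot both be true.

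**How large the loss could be under the literal reading.** Let p be the share of subjects who react and are withdrawn before Visit 2. Every value of p is an assumption.

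- Expected number at Visit 2 = 17 × (1 − p).
- Standard-error inflation = 1/√(1 − p), assuming an unchanged standard deviation.
- Chance of losing at least one subject = 1 − (1 − p)^17.

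| p | Expected at Visit 2 | SE inflation | At least one lost |
|---|---|---|---|
| 0% | 17 | 1.00 | 0% |
| 10% | 15.3 | 1.054 | 83% |
| 30% | 11.9 | 1.195 | 99.8% |
| 50% | 8.5 | 1.414 | about 100% |

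**Skin-type mix at Visit 2.** Enrolled: 7/17, 5/17, 5/17 = 41/29/29% for A/B/C.

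- p = 50/30/10% in A/B/C: 3.5 + 3.5 + 4.5 = 11.5, giving 30/30/39%.
- p = 10/30/50% in A/B/C: 6.3 + 3.5 + 2.5 = 12.3, giving 51/28/20%.
- p = 30% in every group: 4.9 + 3.5 + 3.5 = 11.9, giving 41/29/29%, unchanged.

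The two unequal scenarios move the mix in opposite directions, and nothing in the protocol favours either.

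**Which results are exposed.**

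- Primary endpoint and Visit 1 skin-type comparison: the readings are captured and stored before any later withdrawal, so they are largely unaffected.
- Sunscreen comparison: control, zinc oxide and avobenzone spots lie on the same subject. A withdrawal before Visit 2 removes all three together, so it costs precision and representativeness but does not unbalance the contrast.
- Pigmentation: a subject withdrawn for tanning would already have shown the change. The activity table in Section 7 lists no pigmentation assessment at either visit, so a Visit 2 pigmentation reading lost to withdrawal is hypothetical.
- Time for a reaction to intervene: little if Visit 2 is on the same day, more if it is a month later. The one-week participation in Section 5 suggests that short intervals are typical.

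**The case for a change.** The strongest case for acting is that withdrawal criteria are rules of conduct and belong in the protocol. This one is mandatory and unqualified, and two members of staff could apply it differently to the same tan. The discretionary sentence does not narrow it. Section 10 refers to serious effects only for reporting to the IRB, so it does not narrow it either. A clarification would cost a few sentences and add no visit or subject.

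The textual part of this stands: the term is undefined and no passage exempts the foreseen reactions. The step from there to a design defect does not. It requires choosing the one reading that sets Section 11 against Section 6 when a coherent reading is available. It also requires assuming that reactions are common and that every reactor is removed before Visit 2. The protocol supports neither assumption: it describes the foreseen redness as mild and the doses as no greater than everyday exposure. Section 8 already provides for keeping data collected before withdrawal. How such data are analysed, and how withdrawals are tabulated by group and reason, is ordinary analysis-plan content, and that plan is not at hand.

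**Conclusion.** The concern does not call for a change. Section 11 leaves a term undefined that an investigator can be expected to interpret in light of the pigmentation endpoint. Which reactions warrant withdrawal is a clinical judgement on which this review takes no position. If the sponsor amends the protocol for other reasons, aligning the wording of Sections 6, 11 and 12 would be a harmless tidying.

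The possible effect runs from no loss, if nobody is withdrawn between visits, to a 41% larger standard error at Visit 2 if half the subjects were withdrawn. The skin-type mix could shift in either direction or not at all. These figures rest wholly on assumed rates and on the literal reading. Even then, the effect falls on the precision and representativeness of the Visit 2 data, while the primary endpoint, the Visit 1 skin-type comparison and the within-subject sunscreen contrast remain largely intact.
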